## 8.4.5. Severity Analysis

It is important to distinguish between serious and severe AEs. An AE of severe intensity need not necessarily be considered serious. For example, nausea that persists for several hours may be considered severe nausea, but not a SAE. On the other hand, a stroke that results in only a limited degree of disability may be considered a mile stroke but would be a SAE.

The Investigator will make an assessment of intensity for each AE and SAE reported during the study. AEs and SAEs should be assessed and graded based upon the NCI-CTCAE Version 5.0.

## 8.4.6. Causality Assessment

The investigator's assessment of causality must be provided for all adverse events (serious and nonserious); the investigator must record the causal relationship and answer 'yes' or 'no' to the question 'Do you consider that there is a reasonable possibility that the event may have been caused by the investigational product?'

An investigator's causality assessment is the determination of whether there exists a reasonable possibility that the investigational product caused or contributed to an adverse event.

If the investigator does not know whether or not investigational product caused the event, then the event will be handled as "related to investigational product" for reporting purposes, as defined by the sponsor. If the investigator's causality assessment is "unknown but not related to investigational product", this should be clearly documented on study records.

For SAEs causal relationship will also be assessed for other medication and study procedures. This includes non-treatment-emergent SAEs (e.g., SAEs that occur prior to the administration of investigational product) as well as treatment-emergent SAEs. A protocol-related SAE may occur as a result of a procedure or intervention required during the study (e.g., blood collection). The following guidelines should be used by investigators to assess the relationship of SAEs to the protocol:

• Protocol related: The event occurred due to a procedure/intervention that was described in the protocol for which there is no alternative etiology present in the

subject's medical record.

• Not protocol related: The event is related to an etiology other than the procedure/intervention that was described in the protocol (the alternative etiology must be documented in the study subject's medical record).

#### 8.4.7. Disease Progression

Disease progression can be considered as a worsening of subject's condition attributable to the disease for which the investigational product is being studied. Symptomsand/or signs associated with disease progression should neither be documented as an AE nor be reported as a SAE in an expedited fashion. But according to CTCAE 5.0, death due to disease progression needs to be reported as SAE in an expedited fashion.

#### 8.4.8. New Cancers

The development of a new cancer should be regarded as an SAE. New primary cancers are those that are not the primary reason for the administration of the investigational product and have been identified after the subject's inclusion in this study.

#### 8.5. REPORTING OF ADVERSE EVENTS

Each adverse event is to be assessed to determine if it meets the criteria for serious adverse events. If a serious adverse event occurs, expedited reporting will follow local and international regulations, as appropriate.

#### 8.5.1. Requirements for Serious Adverse Event Reporting

All serious adverse events occurring during clinical study must be reported to the sponsor or its designated representative by investigational staff immediately *within 24 hours* of when he/she becomes aware of it. This timeframe also applies to additional new information (follow-up) on previously forwarded serious adverse event reports as well as to the initial and follow-up reporting of pregnancy cases.

The sponsor representative works with the investigator to ensure that all the necessary information is provided within above timeline.

For all serious adverse events, the investigator is obligated to pursue and provide information to the sponsor in accordance with the timeframes for reporting specified above. In addition, an investigator may be requested by the sponsor to obtain specific additional follow-up information in an expedited fashion. This information may be more detailed than that captured on the adverse event case report form. In general, this will include a description of the adverse event in sufficient detail to allow for a complete medical assessment of the case and independent determination of possible causality. Information on other possible causes of the event, such as concomitant medications and illnesses must be provided.

In the case of a subject death, a summary of available autopsy findings must be submitted as soon as possible to the sponsor or its designated representative.

Once the Investigators or other site personnel indicate an AE is serious in the EDC system, an automated email alert is sent to the designated sponsor representative.

In case EDC is down, facsimile transmission/encrypted email of the filled paper Adverse Event Report form is the preferred backup method to transmit this information to the project contact for SAE receipt. In rare circumstances and in the absence of facsimile equipment, notification by telephone is acceptable, with a hardcopy of the Adverse Event Report form sent by encrypted mail. Initial notification via the telephone does not replace the need for the investigator to complete and sign the paper Adverse Event Report form within 24 hours when he/she aware of the event.

The contact information for assistance with SAE reporting, specific to the site, are listed in the investigator folder provided to each site. The original copy of the Adverse Event Report form and the fax confirmation sheet must be kept with the case report form documentation at the study site.

For details, please refer to the study specific Safety Management Plan (SMP).

The sponsor representative will advise the investigator/study site personnel how to proceed.

The sponsor has a legal responsibility to notify, as appropriate, both the local Health Authority and other regulatory agencies about the safety of a product under clinical investigation. Prompt notification of SAEs by the investigator to the appropriate project contact for SAE receipt is essential so that legal obligations and ethical responsibilities towards the safety of other subjects are met.

The investigator, or responsible person according to local requirements, will comply with the applicable local regulatory requirements related to the reporting of SAEs to regulatory authorities and the Institutional Review Board (IRB) /Independent Ethics Committee (IEC).

#### Abnormal Liver Function Tests

Abnormal liver function that meets the following conditions will be considered as SAE, which shall be reported by the investigator according to the SAE reporting process. If no other criteria are applicable, the important medical serious event criterion could be used for judgment.

- For subjects with normal baseline of AST and ALT and total bilirubin: Treatmentemergent AST or ALT ≥3 × ULN, total bilirubin ≥2 × ULN, ALP < 2 × ULN (or not available) with no evidence of hemolysis;
- For subjects with abnormal baseline ALT or AST or total bilirubin: Treatmentemergent AST or ALT  $\geq 2 \times baseline values and \geq 3 \times ULN$ , or  $\geq 8 \times ULN$ (whichever is smaller) with total bilirubin level increased by at least  $1 \times ULN$  from baseline or if the value reaches  $\geq 3 \times ULN$  (whichever is smaller).

#### Disease progression

Death due to disease progression requires expedited reporting as an SAE per CTCAE 5.0.

New onset of tumors

New onset of tumors should be classified as SAEs. New primary tumor is defined as a tumor found after study enrollment that is not primarily attributable to the use of study drug.

8.5.2. Requirements for Non-serious Adverse Event Reporting

All adverse events will be reported on the adverse event page(s)/module of the eCRF. It should be noted that the form for collection of serious adverse event information is not the same as the adverse

event CRF. Where the same data are collected, the forms must be completed in a consistent manner. For example, the same adverse event term should be used on both forms. Adverse events should be reported using concise medical terminology on the CRFs as well as on the form for collection of serious adverse event information.

#### 8.6. OVERDOSE

Overdose is defined as: the subject has taken (accidentally or intentionally) a dose exceeding the dose prescribed in the protocol by 20%. Subjects with a suspected overdose should be managed with symptomatic treatment or appropriate supportive therapy.

For any drug overdose (whether or not it causes an AE), the investigator should complete a paper Adverse Event Report form within 24 hours of being informed and report it to the sponsor's pharmacovigilance representative. For drug overdoses with AE, AE information shall be recorded and reported together with drug overdose information in accordance with the requirement of Section 8.5.

#### 8.7. PREGNANCY

To ensure subject safety, each pregnancy during study must be reported by the investigator or other site personnel to the sponsor's representatives within 24 hours after being aware of its occurrence. The Sponsor's representatives together with the investigator will ensure that all relevant information is reported to the Sponsor's Pharmacovigilance Representative and the pregnancies and the outcome of each pregnancy in subjects who have been treated with the investigational drug should be reported. Abnormal pregnancy outcomes should be considered as SAEs, which should be reported in the Serious Adverse Event Reporting Form within the appropriate reporting timelimit for SAE.

## 8.7.1. Maternal Exposure

A female becomes, or is found to be, pregnant either while receiving or having been directly exposed to (e.g., environmental exposure) the investigational product, or after discontinuing and/or being directly exposed to the investigational product.

If a subject is found to be pregnant during the study, the study drug should be discontinued immediately.

Pregnancy itself is not regarded as an adverse event unless there is a suspicion that the investigational product under study may have interfered with the effectiveness of a contraceptive medication. Congenital abnormalities/birth defects and spontaneous miscarriages should be reported and handled as SAEs. Elective abortions without complications should not be handled as AEs. The outcome of all pregnancies (spontaneous miscarriage, elective termination, ectopic pregnancy, normal birth or congenital abnormality) should be followed up and documented even if the subject was discontinued from the study.

If any pregnancy occurs in the course of the study, then the Investigator or other site personnel informs the appropriate sponsor representatives within 24 hours of when he/she becomes aware of it.

The same timelines apply when outcome information is available.

The Pregnancy report module in the CRF is used to report the pregnancy (in case of failure of EDC system, the Pregnancy Report Form of sponsor could be filled out for reporting before accessing into the EDC system for supplementation when the EDC system has recovered) and

the Pregnancy Outcome Report is used to report the outcome of the pregnancy.

Pregnancies occurring up to 180 days after the completion of study medication must also be reported to the investigator.

#### 8.7.2. Paternal Exposure

A male has been exposed, either due to treatment or environmental, to the investigational product prior to or around the time of conception and/or is exposed during his partners' pregnancy.

Information on the pregnancy of a subject's partner must be obtained directly from the subject's partner. Therefore, prior to obtaining information on the pregnancy, the investigator must obtain the consent of the subject's partner.

Male subjects should refrain from fathering a child or donating sperm during the study and for 180 days following the last dose.

Pregnancy of the subject's partners is not considered to be an AE. However, the outcome of all pregnancies (spontaneous miscarriage, elective termination, ectopic pregnancy, normal birth or congenital abnormality) should, if possible, be followed up and documented.

To capture information about a pregnancy from the partner of a male subject, the male subject's partner consent must be obtained to collect information related to the pregnancy and outcome; the male subject should not be asked to provide this information. A consent form specific to this situation must be used. The outcome of any conception occurring from the date of the first dose until 180 days after the last dose should be followed up and documented.

# 9. QUALITY CONTROL ,QUALITY ASSURANCE AND DATA MANAGEMENT

#### 9.1. QUALITY CONTROL AND QUALITY ASSRANCE

During trial conduct, CStone or its agent will conduct periodic monitoring visits to ensure that the protocol and Good Clinical Practices (GCPs) are being followed. The monitors will review source documents to confirm that the data recorded on CRFs is accurate. The investigator and institution will allow CStone monitors or its agents and appropriate regulatory authorities direct access to source documents to perform this verification. The trial site may be subject to review by the Institutional Review Board (IRB)/Independent Ethics Committee (IEC), and/or to Quality Assurance audits performed by CStone, and/or to inspection by appropriate regulatory authorities. Such audits/inspections can occur at any time during or after completion of the study.

It is important that the investigator(s) and their relevant personnel are available during the monitoring visits and possible audits or inspections and that sufficient time is devoted to the process.

#### 9.2. DATA MANAGEMENT AND CODING

Data Management will be performed by the sponsor delegated Data Management Vendor.

An electronic data capture (EDC) system will be used for this study. All eCRF data will be entered in electronic forms at the site. Data collection, including all entries, corrections and alterations are to be made by investigator or authorized site personnel designated by the investigator. The eCRF

records will be automatically appended with the identification of the creator, by means of their unique User ID. By entering his/her electronic signature, the investigator confirms that all recorded data have been verified as accurate. All entries to the study database and changes will be fully recorded in a protected audit trail.

The eCRF is essentially considered a data entry form and should not constitute the original (or source) medical records unless otherwise specified. The monitor will review the eCRFs and evaluate them for completeness and consistency by source document verification.

The data will be validated as defined in the Data Management Plan. Data queries will be raised for inconsistent, impossible or missing data. Quality control procedures will be applied to each stage of data handling to ensure that all data are reliable and have been processed correctly. The Data Management Plan will also clarify the roles and responsibilities of the various functions and personnel involved in the data management process.

Adverse events and medical/ surgical history will be coded using the most current version of Medical Dictionary for Regulatory Activities (MedDRA). Medications will be coded using the World Health Organization Drug Dictionary (WHO-DD). All coding will be performed by the vendor.

# 10. QUALITY CONTROL AND QUALITY ASSRANCE

## 10.1. SAMPLE SIZE DETERMINATION

It is planned to enroll not more than 12 subjects in the phase-Ib dose-escalation study. The observed toxicity will decide the actual sample size.

According to efficacy result of BLU-554-1101 study (data cut-off date: 16 Jun 2018), ORR was 17% (11/63) for FGF19 IHC+ subjects (1st line and above) and 0 (0/38) for FGF19 IHC-subjects. ORR of PD-1/PD-L1 monotherapy was reported around 10~20% for 1st line and 2nd line HCC subjects. Based on the data above, BLU-554 in combination with CS1001 is targeting 40% ORR for FGF19 IHC+ subjects and 30% ORR for FGF19 IHC- subjects. Combining the subjects treated at RP2D in Phase Ib and those in Phase II, gating criteria in Bayesian framework are developed as the following:

## Gating based on 25 FGF19 IHC+ subjects

- A non-informative ORR prior is assumed at Beta (0.45, 0.55).
- Timing when all 25 subjects finish at least two post-baseline tumor assessments
- Go 12 responses or more, corresponding ORR 48%, the probability of combo ORR> 40% is 0.788.
- No go 8 (32%) responses or fewer, the probability of combo ORR<40% is 0.797.
- Evaluate 9 (36%) to 11 (44%) responses, evaluate other endpoints, DOR, DCR, safety, etc., and additional 15 FGF19 IHC+ subjects may be enrolled for further evaluation.

# Gating based on 40 FGF19 IHC+ subjects (if enrichment of 15 FGF19 IHC+ subjects as decided)

- A non-informative ORR prior is assumed at Beta (0.45, 0.55).
- Timing when all 40 subjects finish at least two post-baseline tumor assessments
- Go 18 responses or more, corresponding ORR 45%, the probability of combo ORR > 40% is 0.737.
- No go 14 (35%) responses or fewer, the probability of combo ORR<40% is 0.744.
- Evaluate 15 (37.5%) to 17 (42.5%) responses, evaluate other endpoints, DOR, DCR, etc.

## Gating based on FGF19 IHC- subjects treated at RP2D in Phase Ib

- A non-informative ORR prior is assumed at Beta (0.2, 0.8).
- Timing only conducted if at least 6 FGF19 IHC- subjects are treated at RP2D in Phase Ib, when they finish at least two post-baseline tumor assessments
- No go 0 response, the probability of combo ORR<30% is greater than 0.99, Phase II will only include the FGF IHC+ cohort
- Evaluate 1 response or more, the cohort of FGF IHC- subjects will be included in Phase II

## Gating based on 15 FGF19 IHC- subjects

- A non-informative ORR prior is assumed at Beta (0.2, 0.8).
- Timing when all 15 subjects finish at least two post-baseline tumor assessments
- Go 6 responses or more, corresponding ORR 40%, the probability of combo ORR > 30% is 0.757. If the final decision for FGF19 IHC+ subjects is "go", FGF19 IHC- subjects

may also be included in the target population of future development.

- No go 3 (20%) responses or fewer, the probability of combo ORR<30% is 0.845. future development will not include FGF19 IHC- subjects in the target population.
- Evaluate 4 (26.7%) to 5 (33.3%) responses, evaluate other endpoints, DOR, DCR, etc.

The sample sizes of 25 or 40 FGF19 IHC+ subjects and 15 FGF19 IHC- subjects are selected to have reasonably high probability of ORR exceeding the target when the go criteria are met or ORR being lower than the mono therapies when no-go criteria are met.

The go and no-go criteria are set up to guide future development of the combination. They are **not binding** decision-**making rules**.

If the actual numbers of evaluable subjects are different from those planned above, the same method will be used to calculate the posteriori probability that ORR will reach the predefined target for reference in subsequent development.

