probability of combo ORR $> 40\%$ is 0.788.
• No go - 8 (32%) responses or fewer, the probability of combo ORR<40% is 0.797.
• Evaluate - 9 (36%) to 11 (44%) responses, evaluate other efficacy endpoints (DOR, DCR etc.) and safety.
Gating based on 40 FGF19 IHC+ subjects (if enrichment of 15 FGF19 IHC+ subjects as decided)
• A non-informative ORR prior is assumed at Beta (0.45, 0.55).
• Timing - when all 40 subjects finish at least two post-baseline tumor assessments
• Go - 18 responses or more, corresponding ORR 45%, the probability of combo ORR > 40% is 0.737.
• No go - 14 (35%) responses or fewer, the probability of combo ORR<40% is 0.744.
• Evaluate - 15 (37.5%) to 17 (42.5%) responses, evaluate other efficacy endpoints (DOR, DCR, etc.) and safety.
Gating based on FGF19 IHC - subjects treated at RP2D in Phase Ib
• A non-informative ORR prior is assumed at Beta (0.2, 0.8).
• Timing - only conducted if at least 6 FGF19 IHC- subjects are treated at RP2D in Phase Ib, when they finish at least two post-baseline tumor assessments
• No go - 0 response, the probability of combo ORR<30% is greater than 0.99, Phase II will only include the FGF IHC+ cohort
• Evaluate - 1 response or more, the cohort of FGF IHC- subjects will be included in Phase II
Gating based on 15 FGF19 IHC- subjects
• A non-informative ORR prior is assumed at Beta (0.2, 0.8).
• Timing - when all 15 subjects finish at least two post-baseline tumor assessments
• Go - 6 responses or more, corresponding ORR 40%, the probability of combo ORR > 30% is 0.757. If the final

 
decision for FGF19 IHC+ subjects is "go" (Gating based on 15 or 40 FGF19 IHC+ subjects, as above said), FGF19 IHC- subjects may also be included in the target population of future development.
 
No go - 3 (20%) responses or fewer, the probability of combo ORR<30% is 0.845. Future development will not include FGF19 IHC- subjects in the target population.
 

• Evaluate - 4 (26.7%) to 5 (33.3%) responses, evaluate other

efficacy endpoints (DOR, DCR, etc.) and safety.
The sample sizes of 25 or 40 FGF19 IHC+ subjects and 15 FGF19
IHC- subjects are selected to have reasonably high probability of
ORR exceeding the target when the go criteria are met or ORR
being lower than the mono therapies when no-go criteria are met.
The go and no-go criteria are set up to guide future development of
the combination. They are not binding decision-making rules.

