### **Phase II: Dose Expansion**

[figure not shown]
The primary objective of the dose expansion phase is to further evaluate the antitumor efficacy as well as the safety, tolerability, PK and immunogenicity of the combination regimen. Subjects will be enrolled into 2 groups based on FGF19 IHC expression: Group 1 will be HCC subjects with FGF19 IHC-, approximately 15 subjects will be enrolled; Group 2 will be HCC subjects with FGF19 IHC+, approximately 25 subjects will be enrolled, approximately total 40 subjects in expansion part. Data on phase Ib evaluation at RP2D will be used as the basis to determine whether to continue to enroll subjects with FGF19 IHC- in the dose expansion phase. If the statistically pre-specified continuous evaluation range is reached, additional subjects with FGF19 IHC+ may be enrolled for further evaluation. FGF19 IHC test will be performed at central laboratory with FGF19 IHC+ defined as  $\geq 1\%$  for inclusion assessment.

Archived or fresh tumor samples must be provided for FGF19 and PD-L1 IHC test which will be performed at central laboratory. (See Section 错误!未找到引用源。)

The imaging examinations of tumors shall be evaluated in accordance with RECIST v1.1. During the 1st year of the treatment, subjects will receive CT/MRI examination in the screen period and every 9 weeks (at the end of every 3 cycles). After 1 year of study, CT/MRI examinations shall be carried out once every 12 weeks (The investigator may increase the number of tumor evaluations where clinically indicated).

Subjects will be monitored for anti-tumor activity, safety, tolerability, PK profile and host immunogenicity throughout the study from the day of first administration of study drugs up to 90 days after the last administration or up to two-year treatment period of combination regimen.

Figure 12:Study Procedure

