	
baseline tumor assessments
 
 No go - 0 response, the probability of combo ORR<30% is greater than 0.99, Phase II will only include the FGF IHC+ cohort Evaluate - 1 response or more, the cohort of FGF IHC- subjects will be included in Phase II 
Gating based on 15 FGF19 IHC- subjects
 
 A non-informative ORR prior is assumed at Beta (0.2, 0.8). Timing - when all 15 subjects finish at least two post-baseline tumor assessments Go - 6 responses or more, corresponding ORR 40%, the probability of combo ORR > 30% is 0.757. If the final decision for FGF19 IHC+ subjects is “go” (Gating based on 15 or 40 FGF19 IHC+ subjects, as above said), FGF19 IHC- subjects may also be included in the target population of future development. No go - 3 (20%) responses or fewer, the probability of combo ORR<30% is 0.845. Future development will not include FGF19 IHC- subjects in the target population. Evaluate - 4 (26.7%) to 5 (33.3%) responses, evaluate other efficacy endpoints (DOR, DCR, etc.) and safety. 
The sample sizes of 25 or 40 FGF19 IHC+ subjects and 15 FGF19 IHC- subjects are selected to have reasonably high probability of ORR exceeding the target when the go criteria are met or ORR being lower than the mono therapies when no-go criteria are met. The go and no-go criteria are set up to guide future development of the combination. They are not binding decision-making rules. If the actual numbers of evaluable subjects are different from those planned above, the same method will be used to calculate the posteriori probability that ORR will reach the predefined target for reference in subsequent development.

--	---

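### The sample-size rationale describes a No-go as evidence of ORR below the monotherapies, but every No-go probability the plan prints is against the 40% or 30% combination target

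*Protocol*

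**What the plan says.** The rationale closing Protocol 10.1 states that the sample sizes were chosen to "have reasonably high probability of ORR exceeding the target when the go criteria are met or ORR being lower than the mono therapies" when the No-go criteria are met. The Protocol synopsis (1.1, Sample Size Determination) and SAP 2.2 repeat it ("being lower than the mono therapies when no-go criteria are met"), as does SAP Appendix 1 ("ORR being lower than the mono therapies when no-go criteria are met"). So the Go comparator is the target and the No-go comparator is the monotherapies.

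The No-go bullets in Protocol 10.1 use a different comparator:

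- 25 IHC+ subjects: "8 (32%) responses or fewer, the probability of combo ORR<40% is 0.797"
- 40 IHC+ subjects: "14 (35%) responses or fewer, the probability of combo ORR<40% is 0.744"
- 15 IHC- subjects: "3 (20%) responses or fewer, the probability of combo ORR<30% is 0.845"

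No probability against a monotherapy rate is printed anywhere. The monotherapy rates in Protocol 10.1 are 17% (11/63) for BLU-554 in IHC+ subjects, 0/38 in IHC- subjects, and about 10 to 20% for PD-1/PD-L1 agents.

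The 40-subject rule follows from an Evaluate result of 9 to 11 responses in 25, after which "additional 15 FGF19 IHC+ subjects may be enrolled for further evaluation". Protocol 4.1 agrees: "If the statistically pre-specified continuous evaluation range is reached, additional subjects with FGF19 IHC+ may be enrolled for further evaluation". The plan also states that the Go and No-go criteria do not bind.

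**The concern.** This sentence is the plan's only stated justification for 25, 40 and 15 subjects, and it tells the reader what a No-go can be taken to show. The IHC+ No-go boundaries are observed ORRs of 32% (8/25) and 35% (14/40), well above every monotherapy rate the plan quotes. A posterior centred near those values cannot put most of its mass below 20%. Someone relying on the sentence could report a boundary No-go as showing that the combination is probably worse than either drug alone, when the plan's own model says it is probably below 40% and very probably above 20%.

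**Working it through.** **Inputs (Protocol 10.1).** Prior Beta(0.45, 0.55) for IHC+ and Beta(0.2, 0.8) for IHC-. No-go boundaries 8/25, 14/40 and 3/15. Targets 40% and 30%. The monotherapy reference is taken as 20%, the top of the quoted PD-1/PD-L1 range and the choice that most favours the sentence among the rates quoted.

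**Formula.** With x responses in n subjects the posterior is Beta(a + x, b + n − x), and P(ORR < c) is its cumulative distribution function at c.

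**Step 1: the plan's figures, then the same posteriors at 20%.**

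| Boundary | Posterior | P(ORR < target), computed | Printed | P(ORR < 20%) |
|---|---|---|---|---|
| 8/25 IHC+ | Beta(8.45, 17.55) | 0.7972 (40%) | 0.797 | 0.076 |
| 14/40 IHC+ | Beta(14.45, 26.55) | 0.7436 (40%) | 0.744 | 0.013 |
| 3/15 IHC- | Beta(3.2, 12.8) | 0.8452 (30%) | 0.845 | 0.550 |

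The printed numbers are right. They answer a different question from the one the sentence poses.

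**Step 2: sensitivity of the IHC+ boundary values to the reference rate.**

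| Assumed monotherapy ORR | 8/25 | 14/40 |
|---|---|---|
| 17% (11/63) | 0.032 | 0.003 |
| 20% | 0.076 | 0.013 |
| 28% | 0.327 | 0.166 |
| 29.1% (upper exact 95% limit for 11/63) | 0.373 | 0.208 |

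None reaches 0.5. Replacing the prior with Beta(0.4, 0.6), Beta(0.5, 0.5) or Beta(1, 1) moves the 20% values only within 0.059 to 0.079 (8/25) and 0.010 to 0.014 (14/40).

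**Step 3: below the boundary.** P(ORR < 20%) by count:

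- n = 25: 0.163 at 7 responses, 0.304 at 6, 0.489 at 5, 0.686 at 4. It exceeds 0.5 only at 4 or fewer.
- n = 40: 0.341 at 9, 0.492 at 8, 0.648 at 7. It exceeds 0.5 only at 7 or fewer.
- n = 15 (IHC-): 0.793 at 2, 0.948 at 1, 0.998 at 0.

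**Step 4: average over the whole No-go region.** Weight each No-go count by its beta-binomial probability and normalise: Σ w(x)·P(ORR < 20% | x) / Σ w(x).

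| n | Plan's prior | Uniform prior |
|---|---|---|
| 25 | 0.763 | 0.574 |
| 40 | 0.742 | 0.546 |
| 15 | 0.944 | 0.720 |

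For n = 25 under the plan's prior, zero responses carries 31.7% of the weight and the boundary count 6.0%.

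**Step 5: the planned 25-then-40 route.** If the 15 extra subjects are enrolled only after 9, 10 or 11 responses in 25, the total is at least 9, so a No-go can occur only at totals 9 to 14.

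| Total of 40 | 9 | 10 | 11 | 12 | 13 | 14 |
|---|---|---|---|---|---|---|
| P(ORR < 20%) | 0.341 | 0.216 | 0.124 | 0.065 | 0.031 | 0.013 |
| Weight | 0.006 | 0.033 | 0.091 | 0.183 | 0.293 | 0.394 |

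The weighted average is 0.046 (0.037 under a uniform prior). On the same totals P(ORR < 40%) averages 0.829. The target statement holds on this route; the monotherapy statement does not.

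**The case against.** The best defence is that the sentence speaks of the No-go criteria being met, and those are ranges (8 or fewer, 14 or fewer), not single counts. Averaged over the range under the plan's own prior, the probability of ORR below 20% is 0.763 and 0.742, much like the printed values the plan regards as reasonably high. For 25 subjects this makes the literal wording arguable. It weakens on three counts: the average leans on near-zero responses and falls to 0.574 under a uniform prior; the plan itself prints boundary values; and the average for 40 subjects includes totals that the planned route cannot produce.

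A second defence is that the sentence loosely describes operating characteristics. If the true ORR were 17% or 20%, the fixed-n binomial chance of a No-go would be 0.982 or 0.953 with 25 subjects and 0.998 or 0.992 with 40. The IHC+ sample sizes do screen out a combination no better than monotherapy. But that is the probability of a No-go given a low ORR; the sentence claims the reverse, a low ORR given a No-go.

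Third, the practical effect is small. Each bullet names its own comparator, the paragraph after the sentence recalculates against the predefined target, and the criteria are non-binding. All of that stands, and it is why the point is minor. It is also fair that 20% is an assumed reference: the plan gives no first-line BLU-554 rate, although Phase II enrols only subjects without prior systemic therapy.

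**Conclusion.** The inconsistency is real and minor. The rationale and the No-go bullets use different comparators, and for IHC+ subjects they are not interchangeable: 0.797 against 0.076 at 8/25, and 0.744 against 0.013 at 14/40. The sentence overstates what is shown by an IHC+ No-go at or near the boundary, or by one reached through the planned 25-then-40 route. It is more defensible for the 25-subject No-go region as a whole. The IHC- rule is not contradicted against 20%: about even at the boundary and higher at every lower count.

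This rests on treating 20% and 17% as fixed, ignoring their own uncertainty and the difference in treatment line. The 25-then-40 result also assumes that the extra subjects are enrolled only from the Evaluate range and that responses counted at 25 are not later reversed. Totals of 8/40 or fewer would need enrolment outside that range, which the non-binding criteria allow. The effect is on interpretation only: no decision rule, analysis or estimate changes.

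**What to change.** In Protocol 10.1, the Protocol synopsis, SAP 2.2 and SAP Appendix 1, replace the reference to the monotherapies with the comparator the bullets already use: ORR lower than the combination target (40% for FGF19 IHC+, 30% for FGF19 IHC-). This is the preferred change because it needs no assumed reference rate.

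If a monotherapy statement is really intended, state and justify the reference rate, print the probability against it at each No-go boundary (at 20%: 0.076, 0.013 and 0.550), and drop the claim of a reasonably high probability for IHC+.

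Leave the decision rules, sample sizes and printed probabilities as they are. The cost is one phrase in four places, with no extra subjects. The only downside is a slightly less favourable stated rationale.
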